## SCHEMA

We recently conducted a phase I study of Topotecan + Carboplatin administered by 5-day continuous IV infusion along with the PARP inhibitor veliparib in patients with acute leukemias, aggressive myeloproliferative neoplasms (MPNs) and chronic myelomonocytic leukemia (CMML). The response rate was 33% overall but was 64% for patients with antecedent or associated aggressive MPNs or CMML. Based on these results, we now propose a phase II study evaluating the efficacy of the addition of veliparib to topotecan and carboplatin in accelerated phase CMML and MPNs as well as both newly diagnosed and relapsed/refractory CMML- or MPN-related AML. Eligible patients would be randomized between ARM A (Topotecan 1.2 mg/m^2/d + Carboplatin 150 mg/m^2/d continuous IV infusion on days 3-7 plus veliparib 80 mg PO BID Day 1-21) vs ARM B (Topotecan 1.6 mg/m^2/d + Carboplatin 150 mg/m^2/d continuous IV infusion on days 1-5). In conjunction with the clinical trial, we aim to evaluate and validate biomarkers of response defined in our initial Phase I trial that may predict for response to the V/T/C combination.

## 1. OBJECTIVES

### 1.1 Primary Objectives

To estimate and compare the Complete Response/Complete Response with incomplete recovery (CR/CRi) rate of induction therapy with Topotecan/Carboplatin (T/C) with or without Veliparib (V) in myeloproliferative disorder associated leukemias and CMML.

### 1.2 Secondary Objectives

1. To evaluate and compare the toxicities of T/C/V vs. T/C
2. To compare the 2-year disease-free survival (DFS) and overall survival (OS) in response to T/C/V vs. T/C
3. To detect and compare the presence of minimal residual disease (MRD) remaining after T/C/V vs. T/C
4. Evaluate predictive biomarkers of response via assessment of pretreatment impaired homologous recombination via assessment of:
  - a. NGS panel for genes mutated in myeloid malignancies done as standard of care per institution. The Johns Hopkins assay assesses mutations in ABL1, ASXL1, ATM, ATRX, BCOR, BCORL1, BRAF, CALR, CBL, CBLB, CDKN2A, CEBPA, CSF3R, DNMT31, EP300, ERBB2, ETV6, EZH2, FLT3, GATA1, GATA2, GNAS, IDH1, IDH2, IKZF1, JAK2, KDM2B, KDM6A, KIT, KRAS, KMT2D, KMT2C, MPL, NF1, NLRP1, NOTCH1, NOTCH2, NPM1, NRAS, NSD1, NUP98, PDGFRA, PIK3CA, PHF6, PIGA, PTEN, PTPN11, RAD50, RECQL4, RUNX1, SETBP1, SF3BA, SRSF2, STAG2, STAT3, TET2, TP53, U2AF1, WT1 and ZRSR2 genes.
  - b. Functional impairment of DNA damage response via assessment of pretreatment samples for radiation-induced RAD51 foci.
  - c. Topotecan-induced stabilization of topoisomerase I-DNA covalent complexes, which has recently been observed to be a critical predictor of response to combination of a topoisomerase I poison and PARP inhibitor in xenografts
5. To evaluate veliparib exposure and contribution to response (efficacy and toxicity)

## 2. BACKGROUND

### 2.1 *Myeloproliferative neoplasms and CML*

Myeloproliferative neoplasms (MPNs) represent a heterogeneous group of clonal diseases with a common propensity to progress to acute leukemia. Essential Thrombocythemia (ET), Polycythemia Vera (PV), and Primary Myelofibrosis (MF), as well as mixed myelodysplastic/myeloproliferative neoplasms such as Chronic Myelomonocytic Leukemia (CML) are all clonal neoplasms derived from aberrant early hematopoietic precursors but have varied clinical manifestations. Upon progression, they are uniformly refractory to standard acute leukemia therapies, with median survival less than six months.

One common mutation in MPNs, an activating V617F point mutation in the tyrosine kinase JAK2, is found in greater than 80% of cases of PV, 40% of cases of ET, and 30% of cases of MF. JAK2 mutation and overexpression have been associated with increased homologous recombination (HR) and genomic instability. Other alterations conferring an MPN-like phenotype, such as *BCR/ABL* translocations in CML, *FIP1L1-PDGFR* rearrangements in eosinophilic leukemias, and *FLT3* mutations in acute myeloid leukemia, have also been associated with changes in the DNA repair pathways leading to increased genomic instability and drug resistance. For example, even though early studies indicated that RAD51, a critical component of the homologous recombination (HR) pathway, is upregulated in *BCR/ABL*-positive CML cells, subsequent studies demonstrated that repair in these cells is error-prone and leads to mutations and large deletions or insertions. Further analysis traced this genomic instability to several changes, including (i) enhanced tyrosine phosphorylation of RAD51, leading to its aberrant function, (ii) downregulation of BRCA1; (iii) stimulation of single-strand annealing, an error-prone DNA repair pathway; and (iv) other changes in the Fanconi anemia/BRCA pathway that can be reverted by ectopic BRCA1 expression.

### 2.2 **Veliparib (ABT-888)**

Poly(ADP-ribose) polymerase (PARP) inhibitors are a class of antineoplastic agents being widely tested in solid tumors. These agents target PARP1, PARP2, and PARP3, three enzymes that contribute to various aspects of DNA repair. PARP inhibition not only diminishes base excision repair, but also impairs alternative end-joining and accelerates nonhomologous end-joining. In cells with diminished HR, these changes lead to error-prone DNA repair and cell death. In addition, PARP inhibition leads to trapping of PARP1 on DNA, preventing access of downstream repair proteins to sites of DNA damage and providing a potential mechanism for PARP inhibitor-induced killing in HR proficient cells that contain high levels of PARP1 protein. Importantly, chromosome 1q (including the *PARP1* locus at 1q42) is amplified in a subset of chronic phase MPNs and even more commonly in transformed MPNs, providing a potential opportunity for PARP1 trapping even in MPNs without HR defects.

Veliparib (ABT-888) is an orally available, small molecule PARP inhibitor that enhances the cytotoxicity of diverse classes of DNA damaging agents, including ionizing radiation,

alkylating agents, platinating agents and topoisomerase I (topo I) poisons. Studies in AML cell lines and clinical samples demonstrated that veliparib enhanced the antiproliferative and proapoptotic effects of topotecan *in vitro*, whereas no synergy was found with cytarabine or etoposide. Further analysis indicated that the synergy resulted from trapping of PARP1 on the damaged DNA, thereby inhibiting repair downstream of topo I-DNA covalent complex stabilization.

We previously compared the sensitivity of clinical isolates from several BCR/ABL-negative chronic myeloid neoplasms, including CMML, ET, PV and PMF, to normal controls using two different PARP inhibitors in colony forming assays *ex vivo*. Results of this analysis demonstrated that myeloid progenitors from many patients with *JAK2* wildtype MPNs and CMML exhibit enhanced PARP inhibitor sensitivity, which is greatest in those with defective formation of RAD51 foci after DNA damage. These observations support the further study of PARP inhibitors, alone or in combination with other therapies, in certain MPNs and CMML.

### 2.3 Topotecan & Carboplatin

Topotecan and carboplatin induce synergistic cytotoxicity in acute leukemia cell lines and primary AML cells *in vitro*. This observation was the basis for a phase I study of topotecan + carboplatin by five-day intravenous continuous infusion (IV CI) in adults with relapsed or refractory acute leukemia. Oral and gastrointestinal (GI) mucositis were the dose limiting toxicities (DLTs) of this combination. Complete remissions (CRs) were observed at multiple dose levels, including 3 of 6 patients at the maximum tolerated dose (MTD) of topotecan 1.6 mg/m^2/day and carboplatin 150 mg/m^2/day simultaneously for 5 days. A subsequent ECOG Phase II trial of topotecan/carboplatin at this MTD resulted in CRs in 5 of 35 (14%) patients with relapsed and refractory AML, a response rate similar to a mitoxantrone/etoposide/cytarabine- (MEC-) based arm in the same trial. This Phase II trial of topotecan and carboplatin only studied the doses of 1.6 mg/m^2/day topotecan with 150 mg/m^2/day of carboplatin combination. In the phase I study of the combination, there were 21 evaluable patients in the doses below the 1.2 mg/m^2/150 mg/m^2 combination and responses in 3 of these patients (14%). In the dose levels above 1.2/150, there were 14 patients treated with 6 responses (43%). These data should be interpreted with caution, however, as these patients included a mixture of acute myeloid leukemia, acute lymphoid leukemia, myelodysplastic syndrome, and blast crisis CML. Of the 46 patients on this phase I study, only three had antecedent myeloproliferative disorders, which is the study population we are targeting with the present study. In the control ARM B we will use the recommended phase II dose of topotecan (1.6mg/m^2/day) in combination with carboplatin to maximize chemotherapeutic exposure in absence of veliparib.

### 2.4 Rationale

Building on recent demonstrations that veliparib enhances the antineoplastic effects of topotecan and carboplatin, we conducted a study evaluating veliparib incorporation into leukemia induction therapy using a backbone associated with significant DNA damage. Using a standard 3+3 trial design, we dose-escalated veliparib in combination with topotecan + carboplatin in relapsed and refractory acute leukemias, aggressive myeloproliferative neoplasms (MPNs) and CMML. A total of 99 patients were treated with veliparib 10-100 mg orally twice daily on Days 1-8, 1-14 or 1-21 along with continuous infusion topotecan 1.0-1.2 mg/m^2/d +

carboplatin 120-150 mg/m^2/d on Days 3-7. The maximum tolerated dose was veliparib 80 mg twice daily with topotecan 1.2 mg/m^2/d + carboplatin 150 mg/m^2/d. Mucositis was dose limiting and correlated with higher veliparib exposure. The duration of veliparib administration was 8 days during the dose escalation. Veliparib dosing was extended in two MPN/CMM cohorts to 14 and 21 day durations after completion of the topotecan/carboplatin infusion to take advantage of the PARP inhibitor sensitivity and defective DNA repair inherent in some CMM and MPN cells. Veliparib systemic exposure in plasma positively correlated with bone marrow supernatant but not blasts. Overall response rate was 33% (33/99), with 14 CR, 11 CRI, and 8 PR. Patients with antecedent or associated MPNs or CMM had an overall response rate of 64% (14/22). The median survival for patients with antecedent or associated MPN or CMM was 13.3 months vs 5.1 months for those without antecedent myeloid neoplasms. The one-year relapse free survival for MPN and CMM patients was 41% vs 12 % for those without prior MPNs or CMM. Leukemias with baseline DNA repair defects, as evidenced by impaired DNA damage-induced FANCD2 monoubiquitination, had modestly better survival. A single 80 mg dose of veliparib, as well as veliparib in combination with topotecan + carboplatin, induced DNA damage as manifested by histone H2AX phosphorylation in CD34+ leukemia cells, with greater damage being detected in cells from responders. Utilizing the data from the Phase I trial, an exposure-response analysis was performed. Despite shallow exposure-efficacy relationship, doses lower than 80 mg do not exceed veliparib single agent preclinical IC50. Shallow exposure-mucositis relationship also supports the 80 mg dose. Based on benefit/risk assessment, veliparib at a dose of 80 mg BID for at least 14 days in combination with topotecan plus carboplatin is recommended to be studied in patients with advanced MPNs or CMM.

We now propose a phase II study evaluating the efficacy of the addition of veliparib to topotecan and carboplatin in accelerated phase CMM and MPNs as well as both newly diagnosed and relapsed/refractory CMM or MPN-related AML. Eligible patients would be randomized between ARM A (Topotecan 1.2 mg/m^2/d + Carboplatin 150 mg/m^2/d IV on days 3-7 plus veliparib 80 mg PO BID Day 1-21) vs ARM B (Topotecan 1.6 mg/m^2/d + Carboplatin 150 mg/m^2/d IV on days 1-5). In conjunction with the clinical trial, we aim to evaluate and validate potential biomarkers of response defined in our initial Phase I trial or subsequently identified that may predict for response to the T/C/V combination. The dosing of topotecan in ARM B (1.6 mg/m^2/day) chosen for study is the recommended phase II dose of topotecan when given in combination with carboplatin for acute leukemia.

## 2.5 Correlative Studies Background

### 2.5.1. Leukemia Mutation Panel

Molecular analysis of AMLs, MPNs and CMM has revealed a broad array of mutations contained in the malignant clone. Characterization of specific mutations associated with MPN- and CMM-associated acute leukemia in the context of response to therapy has the potential to allow for patient specific therapies with improved efficacy. We intend to use a standard leukemia mutation panel (MDL JHH) to examine the molecular features of the leukemias treated on this study and examine for response predictors in the post-trial analysis.

### 2.5.2. RAD51 Focus forming assay

An impaired DNA damage response, as evidenced by lack of development of RAD51 foci in response to ionizing radiation, was observed in ~40% of MPN samples assayed (Figure 1). This observation suggests that the HR pathway is impaired in those samples. These results are

[figure not shown]

Figure 1

consistent with prior observations of extensive chromosomal and subchromosomal copy number changes in MPN, which are another hallmark of HR deficiency. Because formation of RAD51 foci only provides an assessment of HR pathway integrity upstream of RAD51 and is unaffected by changes downstream, e.g., loss of RAD51C, it is important to emphasize that the results in Figure 1 might underestimate the true frequency of HR repair defects in MPNs.

The causes of this HR pathway dysfunction in MPNs are incompletely

understood at present. Some of the samples with impaired RAD51 foci formation also exhibited diminished formation of H2AX foci (Fig. 1). Because H2AX phosphorylation after double strand breaks typically reflects activation of ATM and phosphorylation of its substrate MDC1, diminished formation of both phospho-H2AX and RAD51 foci might reflect a defect in ATM or its activation as described in other neoplasms. Other samples formed phospho-H2AX foci but nonetheless failed to form RAD51 foci, suggesting one or more defects between these two events in the DNA damage response. Consistent with this heterogeneity, we have previously examined 144 cases of MPN via SNP arrays and found that 26% have heterozygous deletions in genes encoding one or more DNA repair pathway proteins such as *BRCA2*, *ATM*, *FANCC* or *FANCL*. Because the other copy remains intact, however, it is unclear whether these heterozygous deletions cause sufficient changes in protein expression to impact the HR pathway. Accordingly, we have examined a subset of MPN samples for methylation changes in FANC proteins, *ATM*, and *BRCA2* but did not observe frequent changes in methylation that would confer increased genomic instability. *BRCA1* promoter methylation was found in a 6 of 27 samples analyzed but also was not associated with increased sensitivity to PARP inhibition *ex vivo*. Given the apparent relationship between impaired formation of radiation-induced RAD51 foci and PARP inhibitor sensitivity in MPNs and CMM *ex vivo*, we propose to examine this assay as a potential predictor of sensitivity to the T/C/V and T/C arms.

### 2.5.3. Stabilization of topoisomerase (topo) I-DNA covalent complexes

The first step in the action of topo I poisons is stabilization of topo I-DNA covalent complexes. We have recently raised a monoclonal antibody that specifically detects these covalent topo I-DNA complexes. This reagent has confirmed that topo I-DNA covalent complexes are stabilized by platinum agents as well as topotecan. Subsequent studies have demonstrated that staining with this antibody, which can detect covalent topo I-DNA complexes in tumor cells

and normal tissues *in situ*, discriminates between BRCA wildtype patient-derived xenografts that are sensitive vs. resistant to a topo I poison/PARP inhibitor combination (████████ ms. in preparation). These observations provide the impetus for assessing Topotecan-stabilized topo I-DNA covalent complexes in the context of the present trial.

#### 2.5.4 Whole Exome sequencing

Examination of genomic aberrations outside known leukemia mutations may identify somatic genetic mutations conferring sensitivity to PARP targeted therapy. In order to examine both somatic and germline samples, pre-treatment tumor samples along with peripheral blood for t-cell specific germline DNA will be collected and analyzed as part of the ETCTN-DNA-RNA tissue procurement protocol.

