### **3.2 Randomization Eligibility Criteria**

3.2.1 Bone marrow aspirate and/or peripheral blood specimens were submitted to the central lab and site has confirmation by the local institution that the patient meets one of the criteria specified in 3.1.1 above.

3.2.2 Age  $\geq 18$  years. Because no dosing or adverse event data are currently available on the use of veliparib in combination with topotecan and carboplatin in patients  $<18$  years of age, children are excluded from this study, but will be eligible for future pediatric trials.

3.2.3 ECOG performance status  $\leq 2$  or Karnofsky  $\geq 60\%$  (see Appendix A).

3.2.4 Patients must have normal organ function as defined below:

- Total bilirubin	less than 2.0 mg/dL unless due to Gilbert's Syndrome, then less than 5.0 mg/dL
- AST(SGOT)/ALT(SGPT)	less than $5 \times$ institutional upper limit of normal
- Creatinine Clearance	GFR greater than 30 ml/min per modified Cockcroft-Gault formula

3.2.5 Interval of greater than 4 weeks since allogeneic blood or marrow transplantation (BMT) if performed; and absence of active GVHD

3.2.6 The effects of veliparib on the developing human fetus are unknown. For this reason and because PARP inhibiting agents as well as topoisomerase inhibitors and platinating agents are known to be teratogenic, women of child-bearing potential must agree to use adequate contraception (hormonal or barrier method of birth control; abstinence) prior to study entry, for the duration of study participation, and for 6 months following the last dose of study drug. Should a woman become pregnant or suspect she is pregnant while she or her partner is participating in this study, she should inform her treating physician immediately. Men treated or enrolled on this protocol must also agree to use adequate contraception prior to the study, for the duration of study participation, and 4 months after completion of veliparib administration.

3.2.7 Ability to understand and the willingness to sign a written informed consent document.

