9.3.3.4 Site(s) Performing Correlative Study: [REDACTED] laboratory, Mayo Clinic

**9.3.4 Whole Exome Sequencing – Exploratory/Ancillary Laboratory Correlative Study #4.**

9.3.4.1 Collection and Handling of Specimen(s): Gene mutation analysis via whole exome sequencing will be performed at the NCI per attached substudy methods and techniques. Whole exome sequencing will be performed on pre-treatment samples containing 100 ng of DNA previously collected and stored as allowed by protocol. Germline DNA will be obtained thru isolation of T-cells from pre-treatment peripheral blood sampling sent to JHH MDL prior to therapy.

Patients will have 3 ml of peripheral blood collected in a 3 ml lavender EDTA tube. No processing needed. Refrigerate and ship overnight via Federal Express with cold pack. Do not freeze.

9.3.4.2 **Shipping of Specimen(s):** Ship one lavender top tube (3ml peripheral blood) harvested prior to therapy and the Shipping Manifest form, available on the CTSU website, by Federal Express overnight with cold pack to (no receipt on Saturday, Sunday or holidays):

Molecular Diagnostics Lab  
Johns Hopkins Genomics  
[name]  
[name]

Notify the Molecular Diagnostics Lab of the upcoming shipment, preferably 24 hours prior to sending the specimens: [[contact]](mailto:[contact]).

Specimens with an expected delivery day of Saturday, Sunday or holiday may be held refrigerated at 4 degrees C until shipped.

Harvested DNA specimens will be shipped from SKCCC MDL to the MoCha lab.

9.3.4.3 **Site(s) Performing Correlative Study:** DNA libraries for WES will be generated at the central sequencing laboratories by standard procedures. Sequencing will be carried out on an Illumina HiSeq 2500 sequencer and these results will have variant calling through the procedures associated with the Genomic Data Commons. Analysis of sequencing results will be performed at Johns Hopkins. Mutation status will be correlated with clinical outcomes for the patients on study.

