9.3.6.2 Site(s) Performing Correlative Study: [REDACTED] laboratory, Mayo Clinic

## 10. STUDY CALENDAR

Baseline evaluations are to be conducted within 1 week prior to start of protocol therapy. Baseline labs must be repeated if done greater than 7 days prior to C1D1. In the event that the patient's condition is deteriorating, laboratory evaluations should be repeated within 48 hours prior to initiation of the next cycle of therapy.

	Pre-Reg	Pre-Rand	Day1-7								Day 8-13	Day 14 (± 2d)	Day 15-22 (+/- 2d)	Recovery assessment (day 28-42)
Veliparib ARM A			A	A	A	A	A	A	A	A	A		A	A
Topotecan/Carboplatin ARM A					A	A	A	A	A					
Topotecan/Carboplatin ARM B			B	B	B	B	B							
Informed consent	X													
Demographics		X												
Medical history		X												
Concurrent meds		X			X-----X									
Physical exam		X	X			X					X			
Vital signs		X	X			X					X			
Height		X												
Weight		X	X	X	X	X	X	X	X	X	X			
Performance status		X	X											X
CBC w/diff, plts		X	X	X	X	X	X	X	X	X	X	X	X	
Serum chemistry a		X	X	X	X	X	X	X	X	X	X	X	X	
ECG (as indicated)		X												
Tumor Lysis Labs d		X	X	X	X	X	X				X	X (day 22)		
Adverse event evaluation					X-----X									X
B-HCG			X b											
Bone marrow Aspirate/Biopsy c	X										X e			X
Peripheral blood sample g		X g			X g		X g							
Leukemia mutation panel /Whole exome sequencing sample		X												
RAD51 Assay		X												
Pharmacokinetic blood f		X								X	X	X		
WES peripheral blood for T cells		X												

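### Exome sequencing uses blood T cells as the germline reference for every patient, although patients with a prior allogeneic transplant are eligible and their T cells may be the donor's

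*Combined protocol and SAP*

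**What the plan says.** Section 2.5.4 gives the aim of exome sequencing: looking beyond the known leukemia genes "may identify somatic genetic mutations conferring sensitivity to PARP targeted therapy". Both somatic and germline material are to be examined, so "pre-treatment tumor samples along with peripheral blood for t-cell specific germline DNA will be collected and analyzed".

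Section 9.3.4.1 is the operative instruction: "Germline DNA will be obtained thru isolation of T-cells from pre-treatment peripheral blood sampling sent to JHH MDL prior to therapy". It names no other germline source and no exception. The study calendar (Section 10) schedules only a pre-randomization blood draw for this purpose, listed as "WES peripheral blood for T cells".

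Section 9.3.4.3 states that "these results will have variant calling through the procedures associated with the Genomic Data Commons", and then that "Mutation status will be correlated with clinical outcomes for the patients on study".

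On eligibility, criterion 3.2.5 requires an "Interval of greater than 4 weeks since allogeneic blood or marrow transplantation (BMT) if performed; and absence of active GVHD". None of the exclusion criteria in 3.3 removes transplanted patients.

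**The concern.** A paired tumor/normal comparison works only if the normal sample carries the patient's own inherited genome. In myeloid disease without a transplant, T cells are a sensible choice because they generally lie outside the malignant clone. After an allogeneic transplant that reasoning can fail, because the circulating T cells may descend wholly or partly from the donor. The comparison is then between two people's genomes, and inherited differences can be mistaken for acquired ones.

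At stake is the reliability of the exome calls in these patients, and so of the paired somatic/germline frequencies and the mutation-outcome correlation. With at most 60 patients, a handful of unreliable calls is not negligible in an analysis that looks for markers.

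**Working it through.** The documents state no figure to reproduce here. The check is to set the sections side by side and follow the rule as written.

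**1. Can a transplanted patient reach exome sequencing?** Yes. Criterion 3.2.5 admits the patient after more than 4 weeks without active GVHD, Section 3.3 does not exclude the patient, and 9.3.4.1 applies to all patients.

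**2. What happens at each locus?** Take recipient-derived leukemia and fully donor-derived T cells:

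| Inherited variant in recipient | Inherited variant in donor | Tumor sample shows it | T-cell reference shows it | Result under 9.3.4 |
|---|---|---|---|---|
| yes | yes | yes | yes | germline, correct |
| no | no | no | no | no call, correct |
| yes | no | yes | no | can be called somatic, wrong |
| no | yes | no | yes | recorded as the patient's germline, wrong |

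A truly acquired mutation is still seen as somatic. The errors are confined to loci where donor and recipient differ.

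**3. What limits the error?**
- With mixed T-cell chimerism the reference holds some recipient DNA, so only some of the differences would be miscalled.
- Filters against common inherited variants would remove part of the false somatic calls. Section 9.3.4.3 refers to Genomic Data Commons procedures but gives no rule for post-transplant samples.
- If the leukemia is itself donor-derived, tumor and reference share an origin and the false somatic calls do not arise.

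**4. Is there a safeguard?** I looked in the eligibility criteria (3.1 to 3.3), the exome sections (2.5.4, 9.1, 9.3.4), the calendar (10), the biomarker analyses (13.5, 13.6) and Appendix C. There is no non-blood or donor sample, no chimerism test, no exclusion of transplanted patients from the exome analysis and no sensitivity analysis without them. Appendix C does warn about germline variants, but for the separate leukemia mutation panel. Two documents that the protocol relies on were not available: the attached substudy methods cited in 9.3.4.1 and the tissue procurement protocol cited in 2.5.4.

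**5. How many patients?** The documents do not give the share with a prior allogeneic transplant. Purely as an assumption, with the planned 60 patients (40 in Arm A, 20 in Arm B, Section 13.2) and an even spread over the arms:

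- 5%: 0.05 × 60 = 3 patients (2 in Arm A, 1 in Arm B)
- 10%: 0.10 × 60 = 6 patients (4 and 2)
- 20%: 0.20 × 60 = 12 patients (8 and 4)

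Zero is also possible. The number of patients does not give the number of wrong calls, which also depends on step 3.

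**6. What does the result touch?** Section 9.1 labels exome sequencing exploratory. It is not listed under secondary objective 4, which names the mutation panel, RAD51 foci and topoisomerase I-DNA complexes. Sections 13.5 and 13.6 give no exome analysis. Its link to outcome is the single statement in 9.3.4.3.

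**The case against.** The strongest reply is that the rules may sit in documents outside the protocol text. Handling of post-transplant samples would naturally belong in the substudy methods or the tissue procurement protocol. This stands as a limit: one can say that the available text has no safeguard, not that none exists. If one does exist, a cross-reference in 9.3.4 settles the point.

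The second reply is that the affected group may be tiny. Section 3.1.1 includes newly diagnosed AML and accelerated-phase disease, and limits relapsed or refractory AML to at most two prior inductions. That is fair, and no prevalence can be claimed. But the protocol contains a criterion written for transplanted patients, so their enrollment is foreseen.

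The third reply is that an analyst could set these patients aside later, since transplant history must be known for 3.2.5. That is true, and it is why the fix is cheap. It does not replace a stated rule: followed as written, 9.3.4 uses the wrong reference and keeps the patients in the correlation.

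A reader might go further and infer that the miscalls are tied to outcome, because transplanted patients are more heavily treated and may respond differently, so that a marker association would be created or hidden in a predictable direction. The documents do not support this. They report no response by transplant history, and miscalls unrelated to outcome would mainly add noise. Nor do they support the inference that every post-transplant patient would be falsely positive for a DNA-repair variant: chimerism, filtering and the origin of the leukemia all bear on that.

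**Conclusion.** The inconsistency is real and narrow. As written, 9.3.4.1 and 2.5.4 apply a T-cell germline reference to patients in whom it may be partly or wholly the donor's, and 9.3.4.3 carries the resulting calls into the correlation with outcome. In recipient-derived leukemia this can produce false somatic calls and wrongly attributed germline variants.

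The size cannot be fixed from the documents. It rests on the number of transplanted patients enrolled, the degree of T-cell chimerism and the variant filtering, none of which is given. The conclusion also assumes that the two unavailable documents hold no safeguard, which should be checked first.

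The consequence stays within one exploratory analysis. The primary CR/CRi comparison, its power and its one-sided 0.10 level do not use exome data. The point is worth correcting because the remedy is simple, not because the trial's main conclusions are at risk.

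**What to change.** First check the substudy methods and the tissue procurement protocol. If they already deal with post-transplant samples, cite the rule in 9.3.4.

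If not, state in 9.3.4, and mirror in 2.5.4, that:

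- T-cell DNA is not used as the germline reference for a patient with a prior allogeneic transplant.
- Pre-transplant or non-blood DNA that already exists is used instead where available.
- Otherwise the exome result is reported as tumor-only and labelled so, and the patient is left out of the paired somatic/germline frequencies and of the exome mutation-outcome correlation.
- The number of patients affected is reported.

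The cost is a few lines of text. Transplant history is already needed for 3.2.5, and no new sample, procedure or eligibility change is required. The downside is that a few patients may drop out of one exploratory analysis.
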